17.6 Evaluations of Primary and Secondary Endpoints

The primary and secondary endpoints will be evaluated for the intent-to-treat and per protocol patient populations. The primary comparisons will be the serum concentration of AZD7442 at Days 30, 90, 180, 270 and 360 post-baseline. Serum concentration comparisons of the log-adjusted serum AZD7442 concentration will be analyzed using linear mixed models for repeated measures. Models will include disease category, overall dose, and dose/kg accounting for concomitant treatment regimen category along with appropriate treatment and time interactions. An unstructured covariance matrix will be assumed, however, in the event of non-convergence, compound symmetry, and AR (1), covariance structures will be attempted, in that order. The Least Square Means Differences, and their 95% CIs, will be reported for each timepoint (e.g., Days 30, 90, 180, 270, and 360 post-treatment).

Additional comparisons for Quality of Life (QoL) will be made between the disease category cohorts and concomitant treatment regimen categories. The disease category cohorts are solid tumor cancers and hematologic cancers. Concomitant treatment regimen categories will be defined as chemotherapy only, immunotherapy

only, targeted therapy only, other therapy/ combination therapy only. Differences in the primary endpoints will be assessed using a two-sided statistical significance level of 0.01, adjusting for planned multiple comparisons. All other differences will be assessed using a two-sided statistical significance level of 0.05.

The secondary endpoint comparisons will be made:

- between concomitant treatment regimen categories and
- between disease category cohorts

The between concomitant treatment regimen categories will account for the between disease category analyses. These secondary endpoint comparisons will be made using a logistic regression or linear mixed model accounting for potential patient and disease factors where appropriate. Additional secondary endpoints are as noted previously. The secondary endpoints will be analyzed for the Intent-To-Treat (ITT) population with a Per-Protocol (PP) sensitivity analysis.

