
Clinical Hypotheses to be Evaluated
	
The primary clinical hypothesis to be evaluated is that in patients treated for either solid tumor or hematologic malignancy cancer, a dose of AZD7442 600 mg IM or IV every 6 months will prevent symptomatic SARS-CoV-2 infection including SARS-CoV-2 related hospitalization and/or SARS-CoV-2 related death, independent of type of cancer therapy up to 12 months post-dose. The possibility of a break-through SARS-CoV-2 infection may be influenced by type of cancer, current cancer treatment or length of time post-baseline administration of AZD7442.
 
2.2 Serum Concentrations of AZD7442
 
We hypothesize that serum concentrations of AZD7442 will not be different between solid tumor or hematologic malignancy treatment regimens at any time point post-baseline. We believe that serum concentration of AZD7442 may be correlated with IgG antibody level to SARS-CoV-2 and CD4/CD8 level as a measurement of T-Cell function as well as symptomatic SARS-CoV-2 infection, including SARS-CoV-2 related hospitalization and/or SARS-CoV-2 related death. We also expect to find that AZD7442 side-effects will not be significantly different between the four strata of cancer therapy (chemotherapy only, immunotherapy only, targeted therapy only, other therapy/combination therapy only).
 
2.3 T-Cell Function
 
We hypothesize that T-cell function obtained at Day 30 post AZD7442 administration in cancer patients will be within the normal range compared to historical healthy control patients' CD4/CD8 data. In addition, we hypothesize that patients who experience breakthrough SARS-CoV-2 infection will have an increase in T-cell function compared to data acquired on Day 30 post AZD7442 administration and that this increase will be in the range of expected results in historical control patients.

3.0 Study Objectives
	
3.1 Primary Objective:
 
The primary objective is to quantify the serum concentration of AZD7442 at 1,3, 6, 9 or 12-months post-baseline in all qualified cancer patients treated with AZD7442 600 mg IM or IV every 6 months.
 
3.2 Secondary Objectives:
 
The secondary objectives of the study are as follows:

- Compare the incidence of symptomatic SARS-CoV-2 infection including SARS-CoV-2 related hospitalization and/or SARS-CoV-2 related death between solid tumor and hematologic malignancy patients.

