13.2 Primary Endpoint Assessment

AZD7442 serum concentrations at 30, 90, 180, 270 and 360-days post-baseline will be assessed using a mixed model for repeated measures. The primary endpoint will be analyzed for the Intent-To-Treat (ITT) and Per-Protocol (PP) populations.

**14.0
Secondary
And Exploratory
Endpoints:
Overall Study**

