
17.0 Statistical Considerations
	
17.1 Sample Size Estimation
 
This program will recruit approximately 1,500 treated cancer patients divided into approximately 1,200 qualified solid tumor and 300 qualified hematologic malignancy patients from approximately 75 hematology/oncology medical practice locations throughout the United States. It is expected that on average, each site will enroll 16 solid tumor and 4 hematologic malignancy patients.
 
17.2 Sample Size Power
 
With a sample size of 1500 patients, the power to detect a non-inferiority margin of 5 mcg/ml with a standard deviation of 25 mcg/ml and Type I error rate of 1% is estimated to be approximately 80% when comparing the serum concentration levels between solid tumor and hematologic malignancy groups. The assumed comparison is between 1200 solid tumor and 300 hematologic malignancy patients. A target sample of 1500 patients will provide adequate size to analyze all of the secondary endpoints identified in the baseline and follow-up patient experience/COA surveys and the QoL surveys.
 
At the time of interim analysis, the power to detect a 5 mcg/ml non-inferiority margin with a standard deviation of 25 mcg/ml and Type I error rate of 1% is estimated to be approximately 45%. This assumes a sample of 600 solid tumor and 150 hematologic malignancy patients.
 
17.3 Stratification
 
This is an open-label, pragmatic, multi-center study of participants receiving AZD7442 600 mg IM or IV for prevention of symptomatic SARS-CoV-2 infection including SARS-CoV-2 related hospitalization and/or SARS-CoV-2 related death.

Patients will be stratified based on type of cancer (solid tumor vs hematologic malignancy) with additional stratification for concomitant treatment regimen of chemotherapy only, immunotherapy only, targeted therapy only and other therapy/combination therapy. It is assumed that 80% of enrolled cancer patients will have solid tumors. Patients will be sub-stratified by: currently on active treatment, ≤ 3 months post-treatment or > 3 months and ≤ 12 months post-treatment.

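### Section 17.6 makes five visits primary without saying which decides, and its two-sided 0.01 test does not give the 80% power stated in 17.2

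*Protocol*

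**What the plan says.** Section 13.1 defines the primary endpoint as serum AZD7442 concentration at Days 30, 90, 180, 270 and 360. Section 17.6 gives all five visits the same rank: "The primary comparisons will be the serum concentration of AZD7442 at Days 30, 90, 180, 270 and 360 post-baseline". It sets the level as follows: "Differences in the primary endpoints will be assessed using a two-sided statistical significance level of 0.01, adjusting for planned multiple comparisons". On populations, 13.2 says: "The primary endpoint will be analyzed for the Intent-To-Treat (ITT) and Per-Protocol (PP) populations".

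Section 17.2 sizes the study on a non-inferiority margin of 5 mcg/ml, an SD of 25 mcg/ml and a 1% Type I error with no sidedness given. The resulting power "is estimated to be approximately 80% when comparing the serum concentration levels between solid tumor and hematologic malignancy groups". The group sizes are explicit: "The assumed comparison is between 1200 solid tumor and 300 hematologic malignancy patients". For the interim (600 and 150 patients) it gives about 45%. It mentions no visit and no multiplicity.

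Section 2.2 states: "We hypothesize that serum concentrations of AZD7442 will not be different between solid tumor or hematologic malignancy treatment regimens at any time point post-baseline".

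The solid tumor versus hematologic comparison of concentrations is a secondary objective in 3.2 and a secondary endpoint in 14.1. The primary objective in 3.1 is only to quantify concentrations in all patients.

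**The concern.** Sections 2.2, 17.2 and 17.6 do not describe one test. The power statement covers one comparison, the analysis section has five of equal rank, and the hypothesis covers every visit. No section names a lead visit, an average over visits, or the number of visits that must succeed.

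Two things are at stake. First, results may differ between visits, and the rule for reading them would then be chosen in an open-label study after the data are seen. Second, the stated 80% and 45% may not belong to the test that will be run, in which case readers of the sample size section would think the comparison better powered than it is.

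**Working it through.** **Inputs.** From 17.2: margin 5 mcg/ml, SD 25 mcg/ml, 1,200 and 300 patients (interim 600 and 150), Type I error 1%. From 17.6: five visits, two-sided 0.01. Assumed, because the protocol does not give them: true difference 0, no missing data, the same SD and margin at each visit and, for joint power only, the between-visit correlation.

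**Step 1: standardised margin.** SE = SD × √(1/n₁ + 1/n₂) and z = margin/SE.
- Final: SE = 25 × √(1/1,200 + 1/300) = 1.614, so z = 5/1.614 = 3.098.
- Interim: SE = 25 × √(1/600 + 1/150) = 2.282, so z = 5/2.282 = 2.191.

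**Step 2: reproduce the stated power.** Power = Φ(z − c), where c is the critical value.
- One-sided 1%, c = 2.326: Φ(0.772) = 78.0% final and Φ(−0.135) = 44.6% interim. These fit the stated 80% and 45%.
- Two-sided 1%, c = 2.576: Φ(0.522) = 69.9% and Φ(−0.385) = 35.0%. These fit neither figure.

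The stated powers are therefore for one comparison at one-sided 1%.

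**Step 3: one given visit under the level in 17.6.**

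| Reading of 17.6 | Per-visit level | c | Final | Interim |
|---|---|---|---|---|
| 0.01 is already adjusted (0.05/5) | two-sided 0.01 | 2.576 | 69.9% | 35.0% |
| 0.01 is the overall level, split over five | two-sided 0.002 | 3.090 | 50.3% | 18.4% |

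The interim entries carry the same per-visit level over to the interim.

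**Step 4: all five visits must succeed.** This follows from reading 2.2 as a non-inferiority claim at each visit. No alpha split is then needed. The results are for the final sample, from simulation of five equally correlated normal statistics with mean 3.098 (1,000,000 draws).

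| Assumed correlation | Two-sided 0.01 | One-sided 1% |
|---|---|---|
| 0 | 17% | 29% |
| 0.5 | 37% | 48% |
| 0.7 | 45% | 56% |
| 0.9 | 56% | 66% |
| 0.99 | 66% | 75% |

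A hand check at correlation 0: 0.699⁵ = 0.167 and 0.780⁵ = 0.289.

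**Step 5: is 0.01 plausible as an adjusted level?** Five independent tests at 0.01 have a family-wise error of 1 − 0.99⁵ = 4.9%, and less if they are positively correlated. That is consistent with 0.05 overall.

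**The case against.** The strongest reply is that 0.01 is 0.05 divided by five visits. On that view 17.6 has already adjusted, the 1% in 17.2 matches it, and the split to 0.002 is the reviewer's invention. The reading is natural and cannot be excluded, so the 50.3% and 18.4% are conditional on the other one. It does not rescue the power statement: 17.6 makes the level two-sided, and a given visit then has 69.9%.

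A second reply is that non-inferiority is one-sided by nature, so 78% is right. That would be fair if 17.6 said so, but it fixes a two-sided level and speaks of differences.

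A third is that success at any one visit might suffice. At two-sided 0.01 that has 74% to 99.8% power over correlations 0.99 to 0. No section states such a rule, and it does not match 2.2.

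A fourth is that the primary objective is descriptive, that 2.2 is not labelled as a success criterion, and that the adjustment method is ordinary SAP content. All three are true. The missing method is not criticised here. The conflict is between figures and rules that the protocol itself fixes.

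A reader might also infer a fault in analysing both ITT and PP. Using both is defensible for a non-inferiority question.

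**Conclusion.** The point holds in this form: five primary comparisons with no deciding visit, and a power figure that 17.6 as written does not deliver for any given visit. The shortfall is from about 80% to 69.9% (interim from 45% to 35.0%) if 0.01 is per visit, and to 50.3% (18.4%) if 0.01 is overall. If every visit must succeed, power is below 80% at every correlation tried, whichever sidedness is used.

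These results keep the 17.2 inputs and assume a true difference of 0 and no missing data. They also carry a margin in mcg/ml into an analysis that 17.6 runs on log-adjusted concentrations. The all-five figures rest on an assumed correlation and should be read only as a range.

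Two stronger inferences are not supported. One is that the 1% in 17.2 is definitely unadjusted, so that power is definitely near 50%; the text allows 0.01 to be the adjusted level. The other is that the family-wise error is out of control; five tests at 0.01 stay within 5%, which is excessive only if 0.01 was meant as the overall level.

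**What to change.** In 17.6, choose one of two rules:
- name the one visit that decides the solid tumor versus hematologic comparison, and test the other four in a fixed written order at the same level, stopping at the first failure; or
- state that all five visits must succeed, with no alpha split.

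Say whether 0.01 is the per-visit or the overall level. Use the same sidedness in 17.2 and 17.6.

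Restate the power in 17.2 for the chosen test. For one visit at two-sided 0.01 it is about 70% final and 35% interim. For all five, give a range with the assumed correlation stated.

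Reconcile the status of the contrast: it is powered in 17.2 and secondary in 3.2 and 14.1, while 3.1 only quantifies concentrations. ITT and PP can both stay.

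The cost is wording, a visit chosen in advance, and a less favourable stated power. No extra patients are needed. Only if the sponsor wanted to keep 80% for one visit at two-sided 0.01 would the sample grow, to 365 + 1,460 = 1,825.

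### The trial is powered for a raw-scale non-inferiority margin of 5 mcg/ml, but the planned analysis is a difference test on log concentrations that does not test that margin

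*Protocol*

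**What the plan says.** Three sections of the protocol bear on the comparison of serum AZD7442 between disease groups.

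- **Section 2.2 (hypothesis):** "We hypothesize that serum concentrations of AZD7442 will not be different between solid tumor or hematologic malignancy treatment regimens", and this is meant to hold at every post-baseline timepoint.
- **Section 17.2 (sample size):** it gives "the power to detect a non-inferiority margin of 5 mcg/ml with a standard deviation of 25 mcg/ml" and a 1% type I error, and the power "is estimated to be approximately 80% when comparing the serum concentration levels between solid tumor and hematologic malignancy groups". The sizes behind this figure are 1,200 in the solid tumor group and 300 in the other. For the interim analysis the stated power is about 45%: "This assumes a sample of 600 solid tumor and 150 hematologic malignancy patients". Section 17.2 does not say whether the 1% is one- or two-sided, which group must not be inferior, or at which timepoint the margin applies.
- **Section 17.6 (analysis):** the model is set out as follows: "Serum concentration comparisons of the log-adjusted serum AZD7442 concentration will be analyzed using linear mixed models for repeated measures". On what will be shown from it, the section adds: "The Least Square Means Differences, and their 95% CIs, will be reported for each timepoint". Differences in the primary endpoints are judged at a two-sided 0.01 level, with adjustment for planned multiple comparisons, and all other differences at a two-sided 0.05.

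Non-inferiority appears only in 17.2. Section 15.1, on the interim analysis, asks only for comparisons between disease categories.

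**The concern.** The hypothesis, the sizing and the analysis describe three different things: no difference, non-inferiority within an additive margin, and a test for a difference on a multiplicative scale. The protocol's only power statement therefore supports a test that the analysis section does not contain.

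Two consequences follow. First, a difference of log means back-transforms to a ratio. It cannot be compared with 5 mcg/ml without a reference mean, and the protocol gives none. Second, the only decision rule that is stated rejects equality. Failing to reject is weak evidence for 2.2, and it becomes easier to reach as the sample shrinks or the level is tightened. A non-inferiority test behaves the opposite way.

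**Working it through.** **Inputs, all from 17.2 and 17.6.** Margin d = 5 mcg/ml; SD = 25 mcg/ml; 1,200 vs 300 patients (final) and 600 vs 150 (interim); 1% type I error in 17.2; two-sided 0.01 or 0.05 in 17.6. The normal approximation is used, with a single timepoint and no dropout.

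**Step 1. Standard errors.** SE = SD × √(1/n₁ + 1/n₂).
- Final: 25 × √(1/1200 + 1/300) = 1.614, so d/SE = 3.098.
- Interim: 25 × √(1/600 + 1/150) = 2.282, so d/SE = 2.191.

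**Step 2. Reproduce the stated power.** For non-inferiority with a true difference of 0, power = Φ(d/SE − z).

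| Level | z | Final | Interim |
|---|---|---|---|
| One-sided 1% | 2.326 | 78.0% | 44.6% |
| Two-sided 1% | 2.576 | 69.9% | 35.0% |
| One-sided 5% | 1.645 | 92.7% | 70.7% |
| Two-sided 5% | 1.960 | 87.3% | 59.1% |
| Stated in 17.2 | – | about 80% | about 45% |

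Only the one-sided 1% row fits both stated figures. So 17.2 is a one-sided 1% non-inferiority calculation on the raw scale.

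**Step 3. What the difference test in 17.6 does on the same inputs.** If the groups truly differ by 5 mcg/ml, the chance of a non-significant result is 1 − Φ(d/SE − z):
- two-sided 1%: 1 − 0.699 = 30% (final), 1 − 0.350 = 65% (interim);
- two-sided 5%: 1 − 0.873 = 13% (final), 1 − 0.591 = 41% (interim).

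A one-sided 1% non-inferiority test would pass a margin-sized deficit 1% of the time.

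**Step 4. Interval level.** A one-sided 1% test corresponds to a 98% interval, with half-width 2.326 × 1.614 = 3.75 mcg/ml at the final analysis. A two-sided 1% test corresponds to 99%. The planned 95% interval corresponds to one-sided 2.5%, which is neither.

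**Step 5. If 2.2 means two-sided equivalence within ±5 mcg/ml.** With 1% on each side, power = 2Φ(3.098 − 2.326) − 1 = 56% at the final analysis.

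**Step 6. The margin as a ratio.** Ratio = (m − 5)/m for a reference mean m. The protocol gives no m. For assumed means of 10, 20, 50 and 100 mcg/ml the ratio is 0.50, 0.75, 0.90 and 0.95. The margin therefore cannot be carried to the log scale from the document alone.

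**The case against.** The strongest reply is that this is loose wording and not a failed design. The stated power reproduces. The mixed model will yield a mean difference with an interval at each timepoint, and an analysis plan could add a log-scale margin, a direction and an interval level. The stated primary objective and endpoint (3.1, 13.1) concern concentrations in all patients, and the between-disease comparison is listed as secondary in 14.1. Reporting 95% intervals beside a stricter test is also common practice.

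Much of this stands. The planned intervals could serve a non-inferiority test once those elements are fixed, and the interval level is a minor matter by itself. But the conflict lies between sections of the protocol, so it is not detail left to a later document. The secondary listing in 14.1 also sits uneasily with 17.6, which calls the serum concentrations at the five visits the primary comparisons. It is therefore unclear whether 0.01 or 0.05 applies, which is why both are shown above.

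Some stronger readings are tempting but not supported:

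- A reader might infer that the sponsor will declare the groups not different on a non-significant result. No section says so: 2.2 states a hypothesis, not a decision rule.
- A reader might infer that one additive margin governs every visit from Day 30 to Day 360. Section 17.2 ties the margin to no timepoint, and the protocol gives no concentration values from which to judge how its meaning would change.
- A reader might infer that no analysis of these data could ever address the margin. What is missing is the specification, not the data or the model.

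**Conclusion.** The point holds. Section 17.2 powers a one-sided 1% non-inferiority test on raw concentrations, and 17.6 plans a two-sided difference test on log concentrations, so as written the powered claim is not tested. Against a true difference of 5 mcg/ml, the two-sided 1% rule has about 70% power at the final analysis and 35% at the interim, not 80% and 45%. A non-significant result therefore cannot support 2.2.

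These figures rest on the protocol's SD of 25 mcg/ml, full enrollment in the stated split, a single timepoint and no further multiplicity adjustment. They are raw-scale figures. Power on the log scale needs a log SD and a ratio margin, which the protocol does not give. The contradiction itself depends on none of these assumptions.

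**What to change.** Reconcile 2.2, 17.2 and 17.6 before any concentration data are reviewed. This matters because the study is open-label and has a planned interim comparison.

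**Preferred route: keep non-inferiority.**
- State it as non-inferiority of hematologic malignancy versus solid tumor, with the direction and the timepoint(s).
- Either set one justified geometric-mean-ratio margin for the log-scale model, or keep 5 mcg/ml and make the contrast on the raw scale. Converting 5 mcg/ml mechanically at each visit's mean is not advisable: at an assumed mean of 10 mcg/ml it would accept a ratio of 0.50.
- Conclude from the lower bound of a 98% interval (one-sided 1%).
- Restate power for the test actually used. On the raw-scale inputs it is about 78% at one-sided 1%, about 70% at two-sided 1%, and about 56% if equivalence within ±5 mcg/ml at 1% per side is meant. Recompute with a log SD if the log scale is kept.
- Reword 2.2 to match.

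**Alternative: keep the difference test.** Drop the non-inferiority wording from 17.2, restate the power, and say that a non-significant result will not be read as showing that the groups do not differ.

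The cost is rewording in three sections, a justified margin and a power recalculation. Neither route requires a change to data collection.
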